Single-Session Extraoral Photobiomodulation Reduces Early Postoperative Pain but Not Edema or Trismus After Impacted Mandibular Third Molar Extraction: A Randomized Controlled Trial

ClinicalTrials.gov Identifier: NCT07522918

Date of Document: January 30, 2025

Necmettin Erbakan University, Faculty of Dentistry, Department of Oral and Maxillofacial Surgery

1. Study Design and Ethical Approval

This prospective, parallel-group randomized controlled clinical trial was conducted at Necmettin Erbakan University. The study protocol was approved by the Institutional Ethics Committee for Non-Drug and Non-Medical Device Research (Decision No: 2025/535). Written informed consent was obtained from all participants prior to enrollment.

2. Patient Selection

A total of 70 patients (age range: 17–25 years) with asymptomatic mesioangular impacted mandibular third molars (Pell–Gregory Class IB) were enrolled. Participants were randomized into a PBM group (n=35) or a control group (n=35) using a computer-generated random sequence.

Inclusion Criteria:

- Indication for extraction of an impacted mandibular third molar.
- ASA I status (absence of systemic disease).
- Healthy status of the impacted tooth and surrounding tissues.

Exclusion Criteria:

- Pregnancy or lactation.
- Regular use of NSAIDs or antibiotics within the preceding week.
- Active smoking.

3. Surgical Procedure

All surgical procedures were performed by a single surgeon following a standardized protocol. Local anesthesia was achieved using 4% articaine hydrochloride with 1:100,000 epinephrine. A full-thickness mucoperiosteal flap was raised, followed by standardized bone removal and tooth sectioning under saline irrigation. Wound closure was performed with 3-0 silk sutures. All patients received a standardized postoperative medication regimen including amoxicillin/clavulanic acid, benzydamine HCl/chlorhexidine gluconate mouth rinse, and dexametopfen.

4. Photobiomodulation (PBM) Protocol

The PBM group received a single session of extraoral therapy immediately following surgery using a dual-wavelength GaAlAs laser (650 nm + 904 nm, GRR Laser).

- **Application Time:** 10 minutes.
- **Total Energy:** 270 J (27 J/min).
- **Power Density:** 4.54 mW/cm².
- **Energy Density:** 2.73 J/cm². The probe was positioned in stationary contact over the mandibular angle–ramus region. The control group received no laser application.

5. Outcome Variables

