- **Pain:** Evaluated using a 100-mm visual analog scale (VAS) at postoperative days 2 and 7.
- **Edema:** Measured via facial distance measurements between anatomical landmarks (tragus–labial commissure, gonion–lateral canthus, gonion–labial commissure) at baseline, day 2, and day 7.
- **Trismus:** Assessed by measuring maximum interincisal distance (MID) using a sliding caliper at baseline, day 2, and day 7.
- **Quality of Life:** Evaluated using a 100-mm OHRQoL VAS scale (0 = worst, 100 = normal) at postoperative days 2 and 7.

6. Statistical Analysis

Normality was assessed using Shapiro-Wilk and Kolmogorov–Smirnov tests. Between-group comparisons were performed using Independent Samples t-tests or Mann–Whitney U tests. Repeated measures ANOVA with Bonferroni correction was used for longitudinal data. Significance was set at $p < 0.05$.

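### Edema and trismus have baseline values, but no stated between-group analysis uses them as a covariate, and the plan leaves their role open; the cost is precision, not bias

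*Combined protocol and SAP*

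**What the plan says.** Section 5 (Outcome Variables) defines trismus through interincisal opening: "Assessed by measuring maximum interincisal distance (MID) using a sliding caliper at baseline, day 2, and day 7". Edema is "Measured via facial distance measurements between anatomical landmarks", with three distances taken at the same three visits. Pain and quality of life are recorded only at days 2 and 7, so edema and trismus are the only outcomes with a baseline.

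Section 6 (Statistical Analysis) gives two analyses that could compare the arms: "Between-group comparisons were performed using Independent Samples t-tests or Mann–Whitney U tests" and "Repeated measures ANOVA with Bonferroni correction was used for longitudinal data". The threshold is "Significance was set at $p < 0.05". Neither sentence names a covariate. The section does not say:

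- whether the two-group tests use follow-up values or changes from baseline;
- whether baseline is one of the ANOVA time levels;
- whether the group term or the group-by-time term is the treatment test.

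It gives no SD, correlation, effect size or power. The title nevertheless states a result for these outcomes: "Reduces Early Postoperative Pain but Not Edema or Trismus After Impacted Mandibular Third Molar Extraction".

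**The concern.** Facial distances and mouth opening probably differ between patients for stable anatomical reasons. If so, much of the spread in day-2 and day-7 values was already there before surgery, and the baseline measurement can remove it. A two-sample test on raw follow-up values leaves that spread in the error term.

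The ANOVA may or may not recover it, depending on which term is read. With baseline as a level, the group main effect averages in a visit at which randomization makes the arms equal in expectation, so an effect confined to day 2 is divided by three. The group-by-time test does use within-patient change, but it is an omnibus test and gives no day-2 or day-7 difference with an interval.

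This matters because the title's conclusion on edema and trismus is negative. A non-significant result is informative only if the interval around the difference excludes effects that would matter, and the width of that interval depends on how baseline is used.

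**Working it through.** The plan states no power or sample-size figure, so there is none to reproduce.

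**Inputs from the documents.** 35 patients per arm (section 2: "Participants were randomized into a PBM group (n=35) or a control group (n=35) using a computer-generated random sequence"); significance level 0.05 (section 6).

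**Assumptions.** Two-sided test; true effect 0.5 SD at day 2, where SD is the between-patient SD within an arm; equal variances; the same correlation r between any two visits, from 0.3 to 0.9; approximate normality. The figures are for t- and F-tests; Mann–Whitney was not computed.

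**Two-group comparisons at day 2.** The standard error of the difference, in SD units, is f × √(2/35) = f × 0.239, where

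- raw follow-up value: f = 1;
- change from baseline: f = √(2(1 − r));
- ANCOVA: f = √(1 − r²).

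Power comes from the noncentral t with noncentrality 0.5/(f × 0.239), on 68 degrees of freedom (67 for ANCOVA). Worked at r = 0.7:

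- raw: 0.5/0.239 = 2.09, power 54%;
- change: f = √0.6 = 0.775, 2.09/0.775 = 2.70, power 76%;
- ANCOVA: f = √0.51 = 0.714, 2.09/0.714 = 2.93, power 82%.

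**Repeated-measures ANOVA with baseline as a level.**

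- Group main effect, effect at day 2 only: the effect on the three-visit mean is 0.5/3 = 0.167, and the SD of that mean is √((1 + 2r)/3). At r = 0.7 the SD is 0.894, noncentrality 0.167/(0.894 × 0.239) = 0.78, power 12%.
- Group-by-time: F on 2 and 136 degrees of freedom, noncentrality (35/2) × S/(1 − r), where S is the sum of squared deviations of the three visit effects from their mean. For effects (0, 0.5, 0), S = 0.167; at r = 0.7 this gives 17.5 × 0.167/0.3 = 9.7, power 79%. For (0, 0.5, 0.25), S = 0.125; this gives 7.3, power 66%.

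**Power (%) over the assumed range of r**

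| r | Raw t-test | Change score | ANCOVA | Group×time, day 2 only | Group×time, 0.25 SD left at day 7 | Group main effect, day 2 only |
|---|---|---|---|---|---|---|
| 0.3 | 54 | 41 | 58 | 42 | 33 | 16 |
| 0.5 | 54 | 54 | 66 | 56 | 44 | 13 |
| 0.7 | 54 | 76 | 82 | 79 | 66 | 12 |
| 0.8 | 54 | 90 | 93 | 93 | 84 | 11 |
| 0.9 | 54 | 99.6 | 99.7 | 99.9 | 99 | 11 |

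Simulation with 5,000 trials per setting agreed to within about 2 points. With no effect at any visit, every test rejected in 4.1% to 5.2% of trials.

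**The same loss on other scales.**

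- The smallest effect detectable with 80% power is 0.68 SD for the raw t-test. For ANCOVA it is 0.65, 0.59, 0.49, 0.41 and 0.30 SD in the order of the table.
- ANCOVA with 35 per arm matches a raw comparison with 35/(1 − r²) per arm: about 38, 47, 69, 97 and 184.
- The 95% CI half-width is about 2.0 × 0.239 = 0.48 SD for raw values. Multiplying by √(1 − r²) gives 0.41, 0.34 and 0.21 SD at r = 0.5, 0.7 and 0.9.

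**The case against.** The strongest reply is that the plan may already use baseline well. If it is an ANOVA time level and group-by-time is the treatment test, within-patient change is exploited: for an effect at day 2 only, that test is within about 3 points of ANCOVA at r = 0.7 and level with it above. If the two-group tests are on changes, a natural way to express swelling and mouth opening, they fall about 6 points short of ANCOVA at r = 0.7 and 3 points at r = 0.8. The correlation is also unknown, and at 0.3 ANCOVA gains only about 4 points over the raw t-test. An unadjusted randomized comparison remains valid: type I error is correct, and chance baseline imbalance is already reflected in the standard error.

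All of this stands, and it limits the point. A reader might infer that the planned analyses never take account of baseline; the text does not support that, because it leaves both the scale of the two-group tests and the ANOVA term open. A reader might also infer that the comparisons certainly lose much of their power; that requires raw-value tests, or reading the group main effect, together with a correlation the documents do not give.

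Three things survive. Change scores are never more efficient than ANCOVA, and below r = 0.5 they do worse than ignoring baseline. The group-by-time test trails ANCOVA by 22, 16 and 9 points at r = 0.5, 0.7 and 0.8 if half the effect persists to day 7. And an omnibus p-value cannot show which effects on edema or trismus are excluded.

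**Conclusion.** The point holds as a matter of precision and specification. No stated between-group analysis of edema or trismus uses baseline as a covariate, and the readings that section 6 allows differ widely. At r = 0.7, for a 0.5 SD effect at day 2 only, they run from 12% power (group main effect) through 54% (raw values) and 76% (change) to 79% (group-by-time), against 82% for ANCOVA.

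The sizes rest on 35 per arm with complete data, a two-sided 0.05 test, a 0.5 SD effect, equal correlations between visits and an assumed r. If r is near 0.3 the gain over raw values is minor; from about 0.7 it is large.

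It would be tempting to conclude that the negative result in the title was produced by a weak analysis, or that it is biased. The documents support neither: they report no estimates or intervals and do not show which test was used, and omitting a baseline covariate does not bias a randomized comparison. What can be said is that the plan, as written, does not ensure that a negative finding on these outcomes can be interpreted.

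**What to change.** In section 6, for maximum interincisal distance and for each of the three facial distances, name a baseline-adjusted model as the between-group analysis. This can be ANCOVA at each visit, with group and the baseline value as terms, or one mixed model for the day-2 and day-7 values with group, visit, group×visit, baseline and baseline×visit and an unstructured within-patient covariance. Baseline then enters as a covariate and not as an outcome level.

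Report the adjusted group difference with its 95% CI at day 2 and at day 7, and word the edema and trismus conclusion by the effects that the interval excludes. State what role, if any, the t-test, Mann–Whitney and repeated-measures ANOVA keep for these outcomes, whether on raw or change values, and by which ANOVA term. Because the title already states a result, show the adjusted analysis beside the originally stated ones and mark it as added.

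The cost is a few sentences, one degree of freedom per visit and a re-run on data already collected. No new measurement is needed. The mixed model would also keep a patient who has only one follow-up visit, although the documents do not say whether any visit was missed.

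### With no primary outcome and no adjustment tied to the between-group tests, up to 12 postoperative comparisons carry about a 23–46% chance of some false significant difference and about 12–26% of a false PBM benefit

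*Combined protocol and SAP*

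**What the plan says.** Section 5 lists four outcomes, none ranked above the others:

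- Pain has the entry "Evaluated using a 100-mm visual analog scale (VAS) at postoperative days 2 and 7".
- Edema is followed through three separate facial distances, given as "tragus–labial commissure, gonion–lateral canthus, gonion–labial commissure) at baseline, day 2, and day 7".
- Mouth opening (MID) stands for trismus and is recorded at the same three visits as the facial distances.
- Quality of life has its own 100-mm scale, scored at the two postoperative visits only.

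Section 6 covers the comparison of arms in one sentence: "Between-group comparisons were performed using Independent Samples t-tests or Mann–Whitney U tests". The next sentence reads "Repeated measures ANOVA with Bonferroni correction was used for longitudinal data", and the threshold follows: "Significance was set at $p < 0.05". The section does not list the outcome-by-day comparisons to be tested, state whether tests are one- or two-sided, or define the set of contrasts to which Bonferroni applies.

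The title already states a result: "Reduces Early Postoperative Pain but Not Edema or Trismus After Impacted Mandibular Third Molar Extraction".

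**The concern.** The plan does not say which comparison decides whether PBM works. As written, any between-group comparison with a nominal p-value under 0.05 can be reported as an effect of PBM, and the only named correction is attached to a different analysis. The title then claims success on one outcome in one time window. A reader cannot tell from the plan whether early pain was the question the trial set out to answer or the most favourable of several results. The trial's main positive conclusion depends on that distinction.

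**Working it through.** The plan gives no familywise error rate, power calculation or sample-size derivation, so there is no figure of its own to reproduce except the nominal level of 0.05.

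**Inputs from the documents.** Level 0.05 per test (Section 6); measures and visits (Section 5).

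**Assumptions.** Tests are two-sided, since sidedness is not stated. PBM has no true effect on any outcome. Test statistics are treated as normal with critical value 1.96. The documents give no correlations between outcomes, so a range is shown.

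**Count of postoperative comparisons.** Pain 1 × 2 days = 2; facial distances 3 × 2 = 6; MID 1 × 2 = 2; quality of life 1 × 2 = 2. Total 2 + 6 + 2 + 2 = 12. If the three distances are combined into one measure, 2 + 2 + 2 + 2 = 8. Baseline is not counted because it carries no treatment effect.

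**Independent tests.** For k comparisons, the chance of any false significant difference is 1 − 0.95^k. A two-sided 0.05 test has 0.025 in the direction of benefit, so the chance of at least one false benefit is 1 − 0.975^k.

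- k = 12: 1 − 0.95^12 = 46.0%; 1 − 0.975^12 = 26.2%.
- k = 8: 1 − 0.95^8 = 33.7%; 1 − 0.975^8 = 18.3%.

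**Correlated tests, k = 12** (400,000 simulated draws, common correlation):

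| Correlation | Any false difference | At least one false benefit |
|---|---|---|
| 0 (formula) | 46.0% | 26.2% |
| 0.2 | 42.8% | 22.3% |
| 0.3 | 39.6% | 20.1% |
| 0.5 | 31.8% | 16.0% |
| 0.7 | 23.1% | 11.6% |
| 0.9 | 13.5% | 6.7% |

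**Less uniform correlation.** The structure was also varied: one value between facial distances, one between days for the same measure, one between other measures on the same day, with products of these for different measures on different days. Values of 0.3, 0.3 and 0.1 gave 43.8% and 23.7%. Values of 0.8, 0.7 and 0.5 gave 29.8% and 15.0%. Both lie inside the ranges above.

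**Benchmark.** One pre-specified two-sided test allows 5% in either direction and 2.5% for false benefit. The false-benefit chance is therefore 11.6/2.5 = 4.6 times that at correlation 0.7, and 26.2/2.5 = 10.5 times under independence.

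**After adjustment.** The first Holm step over 12 comparisons is 0.05/12 = 0.0042; over 8 it is 0.05/8 = 0.0063. Testing all 12 at 0.05/12 brings the chance of any false difference to 1 − (1 − 0.05/12)^12 = 4.9% under independence.

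**The case against.** Five points can fairly be made for the plan.

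- **The count is inferred.** This stands. Section 6 lists no tests, and Section 5 does not say whether the distances are analysed separately. The defensible statement is up to 12, with 8 as an alternative. At 8 the inflation is smaller but still well above 5%.
- **The correlations are assumed, and high ones shrink the problem.** This also stands. At 0.9 the figures fall to 13% and 7%, which still exceed 5% and 2.5%.
- **Bonferroni might reach the between-group contrasts.** Every outcome is measured more than once, so all of it could be called longitudinal data. A reader might infer that the correction covers only contrasts over time and gives the arm comparisons no protection; the documents do not say that either. What they support is that the family is undefined. Suppose, generously, that it halved the level for the two postoperative days within each measure. Nothing would then adjust across measures, and with 12 independent comparisons the chances would be 1 − 0.975^12 = 26.2% for any difference and 1 − 0.9875^12 = 14.0% for a benefit.
- **The title also reports null results.** Edema and trismus make up 6 + 2 = 8 of the 12 comparisons, so reporting is not confined to the favourable ones. That is to the authors' credit, but it does not show that pain was chosen beforehand.
- **An earlier record may name a primary.** Section 1 cites an ethics-approved protocol, which is not among these documents. If it names one, most of the concern about the pain claim falls away, so the fix starts there.

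**Conclusion.** The concern holds. No primary outcome or time point is named, one threshold of 0.05 applies, and no adjustment is explicitly tied to the between-group tests. With two-sided tests and no true effect, 12 comparisons give about 23–46% for any false significant difference and about 12–26% for a false PBM benefit, at assumed common correlations of 0.7 down to 0. With 8 independent comparisons the figures are 34% and 18%.

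Two stronger readings are tempting. A reader might take 23–46% as the chance of a false PBM benefit. It is not: that range counts differences in either direction, including apparent harm, and would describe benefit alone only if each test were one-sided at 0.05, which the plan does not say. A reader might also infer that the pain result is a chance finding. The documents give no p-values, so it may well pass 0.0042. They show only that the stated rule cannot separate a planned finding from a selected one.

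**What to change.** Revise Section 6 as follows.

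1. If a record dated before the data were seen (such as the ethics-approved protocol) names a primary outcome and time point, cite it with its date, test that comparison at two-sided 0.05 and apply Holm to the remaining between-group comparisons.
2. If no such record exists, apply Holm across all postoperative between-group comparisons, report every one with its 95% CI, and describe the pain result as exploratory unless it survives.
3. List the comparisons, including whether the facial distances are tested separately or combined, and state that tests are two-sided.
4. State which contrasts the ANOVA Bonferroni covers.

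Pain should not now be designated primary on the strength of this document. Its text is in the past tense and its title already states the pain result, so doing so would formalise the selection in question.

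The cost is some re-analysis of existing data and revised wording. No new data are needed. The downside is that the pain claim and the secondary results may become less favourable.
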